## Participants

This study was conducted with the informed written consent of all the participants and was approved by the appropriate ethics committees (Health and Social Services Center – Sherbrooke University Geriatrics Institute and the Centre hospitalier universitaire de Sherbrooke). Participants underwent a screening visit, including the analysis of a blood sample collected after a 12 h overnight fast. Exclusion criteria included smoking, diabetes (fasting glucose >7.0 mmol/l and glycated hemoglobin >6.9%), unfit to practice exercise, untreated hypertension, dyslipidemia, and abnormal renal, liver, heart or thyroid function. Prediabetic (PD) participants needed to have a fasting plasma glucose of 6.0-6.9 mmol/l and/or a plasma glycated hemoglobin of 6.1-6.4% in order to be eligible to be included in the study (Golderngerg and Punthakee 2013). The Physical Activity Scale for the Elderly (PASE) questionnaire was used as an additional tool to characterise participants' baseline physical activity. To be eligible, participants had to be doing structured physical exercise  $\leq$  two times per week. Participants taking medications known to affect triglyceride or carbohydrate metabolism (*i.e.* diuretics, beta-blockers, steroids, insulin sensitizers) were excluded. Body composition and visceral adipose tissue area were measured by dual-energy x-ray absorptiometry (GE Healthcare LUNAR iDXA, Madison, WI, USA; (Hangartner et al. 2013).

## Experimental design

Participants completed a 4 h metabolic study after each of the four following sequential experimental conditions: (i) no treatment control (CTL), (ii) five days of MCT supplementation alone (MCT), (iii) 30 min of aerobic exercise alone (AE), and (iv) five days of MCT supplementation combined with aerobic exercise (MCT+AE). Participants started with the CTL metabolic study during which they received only the lactose-free skim milk vehicle for the MCT drink. The CTL metabolic study served to set the baseline ketogenic response for the other three experimental conditions. Participants then took the MCT supplement daily for five days; on the fifth day, they repeated the metabolic study, this time with a drink containing 15 g MCT at breakfast. During the second week of the study, participants repeated the metabolic study with vehicle only (such as CTL) but did 30 minutes of AE. This allowed assessment of the effect of a

single acute session of AE on the ketone response during the 4 hour metabolic study. They then did five days of MCT supplementation simultaneously with five days of AE (30 min/day). On the fifth day of the combined intervention, they repeated the metabolic study with a drink containing 15 g MCT at breakfast but also followed by 30 min AE at 1.0 - 1.5 h. The 5 days period of MCT supplementation alone was separated from the MCT+AE period by a 1-3 week washout.

### Metabolic studies

For each metabolic study, the participants arrived at 7:30 a.m. after a 12 h overnight fast and a minimum of 24 h without alcohol intake. A forearm venous catheter was installed and the baseline fasting blood sample withdrawn (Time 0 h). Participants then received a standardized breakfast comprised of two pieces of toast with raspberry jam and the MCT drink or the vehicle, which was 250 ml lactose-free skim milk. Water was available *ad libitum* throughout the study period. Blood samples were taken every 30 min for 4 h in EDTA collection tubes (BD Vacutainer, NJ, USA). Blood samples were centrifuged at 2846 g for 10 min at 4°C and plasma stored at -80°C until analyzed.

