### MCT supplement

The MCT used to make the emulsion was 55% tricaprylin oil (8-carbon MCT) and 35% tricaprין oil (10-carbon MCT; Captex 355, Abitec, Columbus, OH, USA). The emulsion was manufactured under aseptic conditions at Université Laval Laboratory of Food Technologies (Québec, QC, CAN) using our proprietary technology. The emulsion was prepared using 120 g MCT per liter of lactose-free skim milk (12%) and provided to participants in 250 ml bottles. When taking the supplement, participants consumed 15 g of MCT at breakfast (125 ml of the drink) and 15 g again at supper (total MCT 30 g/d; a previously used dose (Courchesne-Loyer et al. 2013) for five consecutive days. Compliance was measured by bottle count.

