### Statistical analysis

The sample size calculation was based on a previous study in which 9 participants were sufficient to measure a significant difference ( $\beta= 0.80$ ) in plasma ketones after consuming 20 g of MCT during a study with the same 4-hour metabolic study period (Vandenberghe et al. 2017b). We recruited  $n=10/\text{group}$  for the present study in case of a dropout during the two weeks. When plasma ketones are present, this refers to the total of AcAc and BHB combined. For all metabolites, the area-under-the-curve (AUC) was calculated according the trapezoid method from 0-4 h during the metabolic study (Gagnon and Peterson 1998). The Shapiro-Wilk test demonstrated that the plasma metabolite data were not normally distributed, so the results of the four conditions were compared using Friedman's test, and the effect of the treatments was determined in each group using Wilcoxon's signed rank test. All statistical analyses were carried out using SPSS 23.0 software (SPSS Inc., Chicago, IL, USA). NG and PD were treated as independent groups and compared using Mann-Whitney's test. Differences were considered statistically significant at  $P\leq 0.05$ . Graphs were prepared using Prism version 6.0 (GraphPad Software Inc., San Diego, CA, USA).

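### On the stated volumes, the 250 ml milk vehicle carries about twice the milk of the 15 g MCT breakfast drink, and no top-up at the MCT visits is described

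*Combined protocol and SAP*

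**What the plan says.** The Metabolic studies section describes a standardized breakfast taken after the fasting sample, with "the MCT drink or the vehicle, which was 250 ml lactose-free skim milk". Experimental design assigns the vehicle to the CTL visit and to the AE visit, where "participants repeated the metabolic study with vehicle only (such as CTL) but did 30 minutes of AE". For the MCT visit, on the fifth supplement day, "they repeated the metabolic study, this time with a drink containing 15 g MCT at breakfast". The MCT+AE visit is described in the same way, with exercise added. Both MCT visits are thus defined by MCT content, without a volume.

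Volumes for the MCT product appear only under MCT supplement. "The emulsion was prepared using 120 g MCT per liter of lactose-free skim milk (12%) and provided to participants in 250 ml bottles". On supplement days, "participants consumed 15 g of MCT at breakfast (125 ml of the drink"), with "15 g again at supper (total MCT 30 g/d; a previously used dose"), for five days.

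On the analysis side, Experimental design says: "The CTL metabolic study served to set the baseline ketogenic response for the other three experimental conditions". The Statistical analysis section computes a 0–4 h AUC for every metabolite and says that "the results of the four conditions were compared using Friedman's test", followed by Wilcoxon signed rank tests within each group.

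**The concern.** A vehicle control should differ from the active drink only in the active ingredient. Here the vehicle volume equals one full bottle of emulsion, which is the whole day's 30 g of MCT. The visit drink carries 15 g, or half a bottle. If that half bottle was drunk as it came, vehicle days included about twice the milk of MCT days.

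The difference would line up exactly with MCT: both vehicle conditions on one side, both MCT conditions on the other. It would run in the same direction for every participant, so neither pairing nor averaging would remove it. The drink is taken after the time 0 sample, so its contribution falls inside the 0–4 h AUC.

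Milk supplies carbohydrate and protein, so the outcomes most exposed are glucose and insulin. Extra milk would be expected to raise both on vehicle days, which could make MCT look as though it lowers them. These outcomes have some weight in a study that compares normoglycemic with prediabetic participants.

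**Working it through.** **Inputs from the documents**
- Vehicle: 250 ml of skim milk (Metabolic studies).
- Emulsion: 120 g MCT per litre, in 250 ml bottles (MCT supplement).
- Breakfast dose: 15 g in 125 ml; daily dose: 30 g (MCT supplement).
- Visit dose: 15 g, volume not given (Experimental design).

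**Assumptions not in the documents**
- Oil density 0.92–0.96 g/ml.
- Carbohydrate in skim milk 4.5–5.5 g per 100 ml.

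**Step 1. Reproduce the plan's figure.** Volume = dose / concentration.
- 15 / 120 = 0.125 l = 125 ml, as stated.
- 30 / 120 = 0.250 l = 250 ml, which is one bottle and also the vehicle volume.

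**Step 2. Milk in the 15 g drink with no top-up.**
- If 120 g is per litre of milk and 15 g goes with 125 ml of milk: ratio 250 / 125 = 2.0. This ignores the oil's own volume.
- If 120 g is per litre of finished drink: oil takes 15 / 0.92 = 16.3 ml to 15 / 0.96 = 15.6 ml. Milk is 125 − 16.3 = 108.7 ml to 125 − 15.6 = 109.4 ml. Ratio 250 / 108.7 = 2.30 to 250 / 109.4 = 2.29.

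The range is 2.0 to 2.3.

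**Step 3. Milk with each way of matching.**
- MCT drink made up to a final 250 ml: milk 250 − 16.3 = 233.7 ml to 250 − 15.6 = 234.4 ml. Ratio 250 / 233.7 to 250 / 234.4, about 1.07.
- Vehicle cut to 125 ml: ratio 125 / 125 = 1.00 on the first reading of Step 2, or 125 / 109.4 = 1.14 to 125 / 108.7 = 1.15 on the second.

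Either way, the remaining difference is at most about 16 ml, the volume displaced by oil.

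**Step 4. Extra carbohydrate on vehicle days, under the assumed milk composition.**
- No top-up: 125 ml × 0.045 = 5.6 g, up to 141.3 ml × 0.055 = 7.8 g (141.3 = 250 − 108.7).
- Made up to 250 ml: 15.6 ml × 0.045 = 0.7 g, up to 16.3 ml × 0.055 = 0.9 g.

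Nothing in the documents converts these amounts into an AUC difference.

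**Step 5. Contrasts touched if there was no top-up.**

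| Contrast | Drinks compared | Milk equal? |
|---|---|---|
| MCT vs CTL | MCT drink, vehicle | No |
| MCT+AE vs CTL | MCT drink, vehicle | No |
| AE vs CTL | vehicle, vehicle | Yes |
| MCT+AE vs MCT | MCT drink, MCT drink | Yes |
| Four-condition Friedman | both | No |

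Two of the three contrasts against CTL are affected. The plan does not name its Wilcoxon pairs; any test of AE against an MCT condition would be affected too. Normoglycemic versus prediabetic within one condition is not, since both groups take the same drink.

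**The case against.** The strongest reply is that no sentence says participants drank 125 ml at a metabolic visit. The 125 ml figure describes taking the supplement in general, and the visit drink is described by content alone. A 15 g dose made up to 250 ml contradicts nothing in the plan. It also fits a breakfast called standardized and a vehicle presented as the counterpart of the MCT drink. This stands: the documents do not establish what was drunk. It does not close the point, because the visit is itself one of the five supplement days, 125 ml is the only volume given for 15 g, and no top-up is described.

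The 250 ml might also be read as covering both drinks. Grammatically it describes the vehicle, and 250 ml of undiluted emulsion would deliver 30 g, against the 15 g stated for the visits.

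It can further be said that the study is sized and framed on ketones, and that MCT versus CTL already differs in added fat, several days of prior supplementation and fixed visit order. Both stand. The first limits the consequence mainly to secondary metabolites. The second means equal milk would not make the contrast clean, but it is no reason to leave in a difference that is so easily removed.

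A reader might infer that a twofold confound has been demonstrated, or that the ketone findings are undermined. The documents support neither: the visit volume is unstated, and no effect on any AUC can be derived from them.

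**Conclusion.** The point holds as a minor one. On the volumes the plan states, the control drink has 2.0 to 2.3 times the milk of the MCT drink, and two of the three CTL-referenced contrasts, together with the Friedman test, carry that difference. This rests on the visit drink being the 125 ml breakfast dose without a top-up, which is the most literal reading but is not confirmed. The upper end of the range also rests on the assumed oil density. If the drink was in fact made up to 250 ml, the ratio falls to about 1.07 and the concern is negligible, though the milk would still not be exactly equal.

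The size of any effect on glucose, insulin or ketone AUCs is unknown. The carbohydrate figures only indicate the scale of the possible imbalance, and they depend on an assumed milk composition.

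**What to change.** Set one drink volume for all four metabolic visits and state it in the Metabolic studies section. Either of two choices works:
- give 125 ml of vehicle at the CTL and AE visits; or
- make the 15 g MCT drink up to 250 ml with the same milk at the MCT and MCT+AE visits.

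This costs one measured volume, with no extra visits or participants.

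The text is in the past tense and already reports a normality test on the data, so the visits were probably complete. In that case:
- If the drink was made up to 250 ml, add one sentence saying so.
- If the volumes were unequal, state that MCT-versus-vehicle effects on glucose and insulin cannot be separated from milk load, and rest the exercise conclusions on AE versus CTL and MCT+AE versus MCT. The cost is one stated limitation; wording cannot repair the data.

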### MCT supplement

The MCT used to make the emulsion was 55% tricaprylin oil (8-carbon MCT) and 35% tricaprין oil (10-carbon MCT; Captex 355, Abitec, Columbus, OH, USA). The emulsion was manufactured under aseptic conditions at Université Laval Laboratory of Food Technologies (Québec, QC, CAN) using our proprietary technology. The emulsion was prepared using 120 g MCT per liter of lactose-free skim milk (12%) and provided to participants in 250 ml bottles. When taking the supplement, participants consumed 15 g of MCT at breakfast (125 ml of the drink) and 15 g again at supper (total MCT 30 g/d; a previously used dose (Courchesne-Loyer et al. 2013) for five consecutive days. Compliance was measured by bottle count.

## Aerobic exercise

During the AE phase of the study, participants exercised for 30 minutes in the morning for five consecutive days, a simple, short protocol feasible for older women. Exercise sessions were supervised by a kinesiologist and were performed on a treadmill or on a stationary bicycle at 55-75% of heart rate reserve, which was calculated as maximum heart rate - resting heart rate using the Karvonen equation (Karvonen and Vuorimaa 1988). Once the participant selected one of the two exercise methods (treadmill or stationary bicycle), it was kept throughout the 5 days of AE. Theoretical maximum heart rate was estimated as  $206.9 - (0.67 \times \text{age})$  (Tanaka et al. 2001) and the resting heart rate was measured before exercise. During the aerobic exercise sessions, heart rate was monitored with a Polar FT2 watch and a T31 heart rate sensor strap (Polar Electro, Kempele, Finland). A physician was on hand in case of a medical emergency.

## Plasma metabolite analyses

Plasma acetoacetate (AcAc) and  $\beta$ -hydroxybutyrate (BHB) were measured by an automated colorimetric assay as previously described (Courchesne-Loyer et al. 2013). Briefly, for AcAc, 25  $\mu\text{L}$  of plasma was mixed with 330  $\mu\text{L}$  of fresh reagent (Tris buffer, pH 7.0, 100 mmol/L, 20 mmol/L sodium oxamate; 0.15 mmol/L NADH and 1U/mL  $\beta$ -hydroxybutyrate dehydrogenase [BHBDH]). For BHB, the reagent was Tris buffer (pH 9.0; 20 mM sodium oxamate, 1 mmol/L NAD, and 1U/mL BHBDH). Tris, oxamic acid, DL-BHB sodium salt, Li-AcAc standard, and NAD were purchased from Sigma (St. Louis, MO, USA), NADH, from Roche (Mannheim, Germany), and BHBDH from Toyobo (Osaka, Japan). The change in absorbance at 340 nm between 15 and 120 s after the addition of the reagent was measured on an automated clinical chemistry analyzer (Dimension Xpand Plus; Siemens, Deerfield, IL, USA). Plasma glucose, lactate, triglycerides (Siemens Medical Solutions USA, Inc., Deerfield, IL, USA) and FFA (Randox Laboratories Limited, West Virginia, USA) were analysed using commercial kits. Plasma insulin was analyzed by enzyme-linked immunosorbent assay (Alpco Diagnostics Ltd., Salem, NH, USA) with a microplate reader (Victor multi-label plate reader 2030; Perkin Elmer, MA, USA). Glycated hemoglobin was measured by HPLC-723G7, a fully automated high

performance liquid chromatography instrument-reagent system (Tosoh Bioscience, King of Prussia, PA, USA).

### Statistical analysis

The sample size calculation was based on a previous study in which 9 participants were sufficient to measure a significant difference ( $\beta= 0.80$ ) in plasma ketones after consuming 20 g of MCT during a study with the same 4-hour metabolic study period (Vandenberghe et al. 2017b). We recruited  $n=10/\text{group}$  for the present study in case of a dropout during the two weeks. When plasma ketones are present, this refers to the total of AcAc and BHB combined. For all metabolites, the area-under-the-curve (AUC) was calculated according the trapezoid method from 0-4 h during the metabolic study (Gagnon and Peterson 1998). The Shapiro-Wilk test demonstrated that the plasma metabolite data were not normally distributed, so the results of the four conditions were compared using Friedman's test, and the effect of the treatments was determined in each group using Wilcoxon's signed rank test. All statistical analyses were carried out using SPSS 23.0 software (SPSS Inc., Chicago, IL, USA). NG and PD were treated as independent groups and compared using Mann-Whitney's test. Differences were considered statistically significant at  $P\leq 0.05$ . Graphs were prepared using Prism version 6.0 (GraphPad Software Inc., San Diego, CA, USA).

